## **9. Interim Analysis**

It is anticipated that our independent safety officer will review the accumulating data at approximately 6-month intervals. Interim data analyses of the key safety and outcome data will be performed in a blinded fashion for each of these data reviews. The primary objective of these analyses will be to evaluate the accumulating data. Our independent safety officer will review the clinical outcome rates, patient recruitment, compliance with the study protocol, reasons and patterns of the missing data, adverse event rates and other factors that reflect the overall progress and integrity of the study.

Before each independent safety officer review session, a blinded summary safety data report will be provided to the safety officer. The extracted data files and the analysis programs for each independent safety officer report will be archived and maintained at the Statistical Data CC for the life of the study.

We will monitor the event rate as it accumulates in a blinded fashion to help us determine if we will achieve sufficient power. We will also review the baseline characteristics of enrolled participants to make sure we have enrolled the population defined in the protocol.

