#### **5. Blinding/medications**

In keeping with a pragmatic trial, this will be an unblinded trial. Since the strategy is patient-activated, we will not enroll more than one patient per household. After knowing the treatment arm randomized to, each patient will watch a video that instructs him/her on how to get the medication he/she is assigned to receive. Although each individual patient or site investigator could know the randomized treatment arm a patient is assigned to, the randomization scheme for the full study will be kept confidential from all the investigators. Randomization scheme will be generated by the unblinded statistician at Duke Clinical Research Institute, and will be implemented by an authorized party who has no involvement in the conduct of the study. This blinding measure aims to eliminate any possibility that the study data is viewed aggregate by randomized treatment before the completion of the trial by anyone outside of the DCRI unblinded statistical team. In order to ensure all the study investigators are unbiased when making decisions during the conduct of the study, it is important to keep them blinded about the possible study results by treatment.

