#### **E. Data Coordinating Center and Statistical Analysis at Duke (Duke Clinical Research Institute (DCRI))**

(DCRI) is a not-for-profit academic research organization (ARO) located in Durham, NC, created by Duke University. DCRI will provide analytic and statistical support and manuscript writing support. DCRI's mission is to facilitate greater academic involvement in clinical research by serving as a leading center of clinical data management and analysis. [name] has extensive experience in designing and performing epidemiological studies and clinical trials and is currently a Professor of Mathematics/Statistics, Biostatistics and Epidemiology at Duke University. [name] was the lead biostatistician for the BELT study and has led analysis of a number of other asthma related trials. DCRI has provided methodological and data analytic support for hundreds of large clinical trials. DCRI will also manage the reports and responses to the independent safety officer. Drs. [name] and [name] have a long and productive working relationship.

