## **B. Risks to Human Subjects**

### **1. Change in medications**

We are adding prn SABA/ICS (PARTICS) to the patient's current therapy. All other changes in patient medications will be made by the patient's personal clinician. Thus, we are not introducing any new medication class to patients' regular daily controller therapy regimen. At baseline, patients will either be on ICS/LABA combination, or on ICS monotherapy, and will be asked to continue their current therapy.

Patients randomized to the intervention arm will be given a prescription filled by central pharmacy and delivered to the patient for an extra ICS inhaler (beclomethasone dipropionate/QVAR® RediHaler™). Included with the ICS inhaler will be a Velcro band to attach to their SABA rescue inhaler to facilitate easy access to both "rescue" medications. Patients will be instructed to take an inhalation of ICS whenever they take a puff of SABA for acute symptom relief but not when the SABA is used as exercise pretreatment. To minimize the risk of overuse of ICS, subjects who are currently having an asthma exacerbation will be considered to be uncontrolled on their current therapy and will be asked to see their physician to re-evaluate treatment options before enrolling in the study. Shared Solutions will contact the central staff if a patient calls for a third refill of QVAR® RediHaler™ (beclomethasone dipropionate HFA) in a month. The central staff will notify the site and the provider will be alerted. All subjects will be informed that the alternative to participation in the trial is to continue their baseline asthma therapies.

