## **6. Data and Safety Monitoring Plan**

We will appoint an independent safety officer from the Division of Pulmonary and Critical Care Medicine from Brigham and Women's Hospital who has no other role in the PREPARE trial. This independent safety officer will be presented data in a blinded manner, and review safety data twice annually.

The PI of the study will be informed of serious adverse events as soon as they occur and will notify the central IRB at Partners within 5 working days/7 calendar days.

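### As most naturally read, the six-monthly safety reviews use pooled data, so they cannot show a between-arm excess of deaths or serious adverse events, and nobody else is given the task of looking for one

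*Combined protocol and SAP*

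**What the plan says.** Section III.E.9 has the independent safety officer review accumulating data about every six months, including clinical outcome rates and adverse event rates. The analyses are described as follows: "Interim data analyses of the key safety and outcome data will be performed in a blinded fashion for each of these data reviews". Before each session "a blinded summary safety data report will be provided to the safety officer". The Data and Safety Monitoring Plan (VII.C.6) agrees: "This independent safety officer will be presented data in a blinded manner, and review safety data twice annually". None of these passages defines blinded.

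Section II.C.5 (Blinding/medications) describes an open-label trial in which the randomization scheme is kept confidential. Its aim is that study data are not "viewed aggregate by randomized treatment before the completion of the trial by anyone outside of the DCRI unblinded statistical team". The stated reason concerns investigators: "In order to ensure all the study investigators are unbiased when making decisions during the conduct of the study".

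Three other passages bear on safety oversight:
- VII.C.6: "The PI of the study will be informed of serious adverse events as soon as they occur", with notice to the central IRB within days.
- VII.B.1: "Shared Solutions will contact the central staff if a patient calls for a third refill of" the study inhaler in one month; the site and provider are then alerted.
- IV.E: "DCRI will also manage the reports and responses to the independent safety officer".

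**The concern.** The officer is asked to look at adverse event rates, and VII.B.2 foresees that total corticosteroid exposure may rise in the intervention arm, at least at first. The safety question that only aggregate data can answer is whether deaths or serious adverse events are more frequent in one arm than in the other. Whether the reviews can answer it depends on one undefined word. If blinded means pooled, the officer sees a single overall rate, and the documents give no reference rate against which to judge it. No one with a stated safety duty would then compare the arms until the trial was over.

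**Working it through.** **1. Which reading do the passages favor?** III.E.9 uses the same phrase about blinding when it describes watching the event rate to check power, and there it most naturally means pooled. II.C.5 restricts by-treatment aggregates to the DCRI unblinded team and makes no exception for the officer. Under VII.C.6 the officer comes from the Brigham and Women's Hospital, so is outside that team. On the pooled reading II.C.5, III.E.9 and VII.C.6 agree with one another. On a coded-arm reading, III.E.9 and VII.C.6 would go against the literal wording of II.C.5. Pooled is therefore the more natural reading, though not the only possible one.

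**2. Does another route fill the gap?** Serious adverse events go to the principal investigator and IRB one at a time. The refill alert concerns one patient. Neither compares rates between arms. The DCRI unblinded team could see an imbalance, but no section tells it to look for one or report it. IV.E does not say which DCRI staff prepare the officer's reports.

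**3. What would a coded table show?** The plan states no safety figure to reproduce. Its power statement (III.E.8) does allow a check of the exposure assumption. With linear loss, mean exposure is 1.25 × (1 − 0.3125/2) = 1.0547 years. Expected events are 600 × 1.0547 × 0.4 = 253.1 in the control arm and 253.1 × 0.765 = 193.6 in the intervention arm. The standard error of the log rate ratio is √(1/253.1 + 1/193.6) = 0.0955. Then |ln 0.765| / 0.0955 − 1.96 = 0.85, which gives 80.1% power against the stated 80%. Linear loss is therefore used below.

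Inputs:
- 605 patients per arm (1210 randomized 1:1).
- Uniform accrual (assumed) over 31 months, October 2017 to April 30, 2020 (Figure 3; II.C.7).
- Follow-up of 15 months, cut at May 1, 2021 (month 43).
- Retained fraction at u months = 1 − 0.25u/12.
- Serious-event rates: not given, so all are assumed.

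Person-months for a patient followed u months = u − 0.25u²/24. At month 24, entrants in months 0–9 have completed 15 months, which gives 9 × 12.656 = 113.9. Later entrants contribute ∫₀¹⁵(u − 0.25u²/24)du = 100.8. Person-years per arm = (113.9 + 100.8) × (605/31)/12 = 349.2.

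Expected z = (r₁ − r₀)√PY / √(r₁ + r₀). For 0.04 against 0.08 at month 24: 0.04 × √349.2 / √0.12 = 2.16, with 14.0 against 27.9 expected events.

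| Month | 6 | 12 | 18 | 24 | 30 | 36 | 42 |
|---|---|---|---|---|---|---|---|
| Person-years per arm | 28.1 | 107.3 | 225.7 | 349.2 | 472.7 | 576.5 | 628.8 |
| z: 4 per 100, ×1.4 | 0.27 | 0.54 | 0.78 | 0.96 | 1.12 | 1.24 | 1.29 |
| z: 4 per 100, ×1.6 | 0.39 | 0.77 | 1.12 | 1.39 | 1.62 | 1.79 | 1.87 |
| z: 4 per 100, ×2 | 0.61 | 1.20 | 1.73 | 2.16 | 2.51 | 2.77 | 2.90 |
| z: 2 per 100, ×2 | 0.43 | 0.85 | 1.23 | 1.53 | 1.78 | 1.96 | 2.05 |
| z: 8 per 100, ×2 | 0.86 | 1.69 | 2.45 | 3.05 | 3.55 | 3.92 | 4.09 |

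Rates are per 100 person-years in the control arm; 4 per 100 is 0.04 × 1.25 = 5% over 15 months. The z-values illustrate sensitivity and are not proposed boundaries.

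**4. What would a pooled report show?** With 1:1 allocation the pooled rate is the mean of the two arms. With 4 per 100 in the control arm it is 4.8, 5.2 or 6.0 per 100 for a 1.4-fold, 1.6-fold or twofold excess. Equal rates of 6.0 in both arms would give the same expected total as 4 against 8.

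**The case against.** A reader might infer that the blinding, interim-analysis and monitoring sections contradict each other and must be reconciled. The documents do not support that. On the pooled reading they agree, and IV.E conflicts with nothing; it is only silent on which team prepares the reports. A reader might also infer that the officer is knowingly barred from by-arm harm data. The wording of II.C.5 reaches that far, but its stated purpose is to keep investigators unbiased, and VII.C.6 gives the officer no other role in the trial.

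The stronger objections concern yield:
- VII.C.4(b) says non-asthma adverse events will not be monitored, and II.C.7 requires no visits after enrollment. Serious adverse events are defined and reported, but capture may be incomplete and, in an open-label trial, may differ by arm. At an assumed 50% capture in both arms, the month-24 value of 2.16 falls to 2.16/√2 = 1.53 and reaches 1.96 only at month 36.
- Even with full capture, a doubling at month 24 has only about a 58% chance of exceeding 1.96 (Φ(2.16 − 1.96)). For deaths alone, at an assumed 1 per 100 person-years, a doubling gives at most z = 1.45.
- Asthma hospitalizations requiring corticosteroids count in the primary outcome (III.B), so a by-arm table of serious events can reveal part of it.
- All patients already have an inhaled corticosteroid prescribed, and single cases can be seen with their assignment.

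These points stand as limits on what the table can do and on how it should be built. They do not fill the gap, because none of them supplies a comparison of rates between arms.

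**Conclusion.** The point holds as a gap in safety monitoring that is cheap to close. On the most natural reading, the officer's reports are pooled and cannot show a between-arm excess of deaths or serious adverse events, and nobody else has the stated duty to compare them. It would be too strong to say that the plan has no safety oversight, since individual serious events are reported promptly and the officer reviews twice a year.

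The gain from a coded table is modest. With 4 per 100 person-years in the control arm and full capture, it would tend to show about a doubling from roughly month 24 and would miss smaller excesses. For a doubling, the expected z is about 2 only by month 36 at 2 per 100, and is already 2.5 at month 18 at 8 per 100. All of this rests on assumed event rates, uniform accrual and equal, complete capture; incomplete capture makes the table less sensitive. That the reports are pooled is an inference from the wording, so confidence is moderate.

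**What to change.** In III.E.9 and VII.C.6, define blinded. State that at each existing review the DCRI unblinded team sends the officer a confidential table of deaths and serious adverse events by coded arm, for harm review only. Add an exception for the officer to II.C.5, and name whom the officer escalates to. List asthma hospitalizations on a separate line or leave them out of the by-arm table, because they overlap the primary outcome; show no other primary-outcome data by arm. Note beside the table that non-asthma adverse events are not monitored, so capture may be incomplete.

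The cost is a few sentences and one small table per review, from the center that already manages the officer's reports. The downside is that one independent person sees limited by-arm data. With the harm-only restriction in writing, no alpha is spent on efficacy.

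The COVID-19 sub-study section (X) and Figure 3 suggest that follow-up may already be over. If no review remains, one or two sentences in the final report should state what blinded meant in practice and whether harm was compared by arm during the trial.

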## 10. Addressing missing data

Every effort will be undertaken to limit premature discontinuations and ascertain completeness of data collection. Based on patient partner and patient advocate feedback, we are providing multiple methods of delivering the forms and multiple ways for participants to respond, including mail, email, telephone, text, smartphone app, website, and voice- response systems. We will also implement procedures designed to retain patients and increase responses. We will reimburse participants for completing forms with levels that our patient advisors felt would encourage completion. For any positive responses regarding exacerbations, we will call to verify and, where available, obtain medical records. We will also use the systems we used in our prior BELT study with AA participants to monitor missing data. Forms that are >10 days delayed result in attempts to re-contact the participant through all available consented modalities.

In concert with intent-to-treat principles, we will continue to attempt to obtain information on patients who failed to return questionnaires. Sites will have access to medical records, claims data and prescription refills. Thus, unless the patient has withdrawn consent, we will be able to continue collecting information on the primary outcome through these alternative means. We will obtain the following information for dropouts: 1) reason for dropping out; 2) primary determiner of dropout; 3) degree of participation. We will use a traditional consort diagram to track the randomized patients. Full sample size will be presented in all tables and figures with clear annotation of the numbers used for each analysis.

For the primary analysis (Andersen-Gill model) subjects discontinuing the study prematurely will be censored at the time of discontinuation. This approach might lead to biased results if discontinuation does not occur at random. Thus, two sensitivity analysis will be undertaken to examine the sensitivity of inference when data is missing at random and not at random: 1. Inverse probability weighting. In this approach, contribution of each subject to the risk set calculated at time  $t$  will be inversely weighted by the estimated probability of remaining uncensored up to time  $t$ . This probability will be estimated using a Cox proportional hazards model fitted to time to censoring with variables potentially prognostic of both, failure and censoring, both baseline and time- dependent (such as most frequent major protocol deviations, certain AEs etc.), entered as covariates. In order to reduce potentially high variability of the resulting treatment effect estimators due to sampling variability in weights, the weights will be “stabilized” by multiplication of probabilities of remaining uncensored up to time  $t$  estimated using baseline covariates only. 2. Pattern-mixture approach. As per Little 2012. we will assume that for participants who drop out, the hazard of an outcome deviates from that of participants who do not drop out by an offset- $r_1$  for treatment and  $r_0$  for placebo. We will then explore the effect of this deviation on the findings for various choices of the offsets in the two study groups. If the treatment effect is qualitatively maintained for the range of offsets that are considered to be clinically plausible, then the findings will be considered to be robust.

In other analyses, missing data will be handled by using multiple imputation. Ten imputed data sets will be generated with imputation methods based on the regression or Monte Carlo framework. Final results will be based on averages from the ten imputed data sets with appropriate estimator employed of the variance. The variables included in the imputation model as covariates will be pre-specified.

### B. Clinical Coordinating Center at Brigham and Women's Hospital

The primary research facility is the Brigham and Women's Hospital (Harvard).

### C. Practice Based Research Networks: American Academy of Family Physicians (AAFP) National Research Network (NRN):

The AAFP NRN is one of the largest practice-based research networks in the country which has focused primarily on pragmatic clinical trials (PCTs) for the past seven years. The AAFP NRN will serve as the clinical coordinating center for this project.

Network studies have resulted in over 90 publications in the past 14 years with a number of papers under review and in development. The AAFP NRN has received funding from NIH,

AHRQ, CDC, and numerous foundations and industry sources. Virtually every PBRN study involves multiple clinical locations with pilots often engaging 8 to 12 sites and full PCTs engaging 20 to 40 sites, thus the AAFP NRN staff routinely supports multi- site trials. The AAFP NRN experience includes the Americans In Motion-Healthy Interventions trial, a 3-year, multi-million dollar trial examining the impact of the AIM-HI approach on improving diet, exercise and emotional well-being on weight, physical fitness, psychological health as well as physiologic and metabolic parameters in over 650 obese individuals cared for in 24 family medicine offices across 15 states ([name] 2013). A second project conducted with the Olmsted Medical Center Research Office (incorporated into the AAFP NRN sub-contract for this project) supported 30 family medicine offices in recruiting, treating and tracking over 2200 recently post-partum women for depression symptoms for a year after enrollment ([name] 2012). This study was only the second to demonstrate improved outcomes with the treatment of post- partum depression. Finally, the entire research core recently completed the BELT study which tracked 1100 African American individuals with asthma for up to 18 months across 20 sites. The AAFP NRN, in conjunction with the core study team, have demonstrated their ability to effectively coordinate large, multi-site PCTs. The AAFP NRN has demonstrated its ability to coordinate multiple clinical sites for a number of large projects.

#### **D. Johns' Hopkins Adherence Center**

[name] is a nationally known expert in the area of medication adherence and the barriers that exist to improving treatment adherence. [name] has been involved previously in a number of asthma studies and will join the research team to guide the work with patient stakeholders and the clinical sites to address identified barriers to adherence to the patient reliever-activated use of ICS.

#### **E. Data Coordinating Center and Statistical Analysis at Duke (Duke Clinical Research Institute (DCRI))**

(DCRI) is a not-for-profit academic research organization (ARO) located in Durham, NC, created by Duke University. DCRI will provide analytic and statistical support and manuscript writing support. DCRI's mission is to facilitate greater academic involvement in clinical research by serving as a leading center of clinical data management and analysis. [name] has extensive experience in designing and performing epidemiological studies and clinical trials and is currently a Professor of Mathematics/Statistics, Biostatistics and Epidemiology at Duke University. [name] was the lead biostatistician for the BELT study and has led analysis of a number of other asthma related trials. DCRI has provided methodological and data analytic support for hundreds of large clinical trials. DCRI will also manage the reports and responses to the independent safety officer. Drs. [name] and [name] have a long and productive working relationship.

## **G. Back-up sites**

Given the budget structure for this project where the majority of a site's budget is dependent on successful recruitment there was a logical limit to the number of clinical sites that could be included. With 1200 patients required for appropriate power we have budgeted for up to 1385 patients being consented. This will allow for some patients who are found to not be eligible after being enrolled and patient drop-out within the first month of the study.

The budget for enrolling patients is fixed and will follow the sites that are successful in their enrollment. To be sure this project successfully meets its enrollment goal (the biggest single problem in most clinical trials) we have also budgeted to be able to on-board 2 additional sites should enrollment fall short. There are currently two other medical systems that have expressed interest in participating that we were not able to include at this time. Jacobi Medical Center in New York City was a component of our last application and Wayne State University asked to be included in this application. Both locations have been told that if there are any enrollment problems they will be added to the clinical performance sites.

